## 6. A Priori Statistical Methods

### 6.1. General Considerations

Statistical analysis of this study will be the responsibility of Eli Lilly and Company (hereafter, Lilly). The statistical analyses will be performed using SAS® Version 9.4 or higher.

Continuous data will be summarized in terms of the number of observations, mean, standard deviation (SD), minimum, median, and maximum. The minimum and maximum will be reported to the same number of decimal places as the raw data recorded in the database. The mean and median will be reported to 1 more decimal place than the raw data recorded in the database. The SD will be reported to 2 more decimal places than the raw data recorded in the database. In general, the maximum number of decimal places reported shall be 4 for any summary statistic.

Categorical data will be summarized in terms of number of patients in the analysis population, number of patients providing data at the relevant time point, frequency counts, and percentages corresponding to the appropriate method. Percentages will be presented to 1 decimal place. Percentages will not be presented for zero counts. For condition/event that is gender-specific (as defined by the Medical Dictionary for Regulatory Activities [MedDRA]), the denominator and computation of the percentage will include only patients from the given gender.

Change from baseline will be calculated as: observed postbaseline scores – baseline score.

For selective efficacy measures (including ASAS40 components, BASDAI score), percent improvement will be calculated as  $100 \times (\text{baseline score} - \text{observed scores})/\text{baseline score}$ , unless otherwise specified. If a patient has experienced an improvement, this measure will be positive. If a patient has experienced a worsening, this measure will be negative.

Unless otherwise specified, baseline for effect in efficacy and health outcomes analyses is defined as the last available value before the first dose of study treatment in Period 2 from the originating study and, in most cases, will be the value recorded at Week 0 from the originating study. For safety analysis, baseline is defined as the last available value before the first dose at the start of each analysis period of interest in RHBY. For safety analyses using a baseline period, the baseline period is defined as the entire period, that there is no drug dispensed in, prior to the first injection of the drug in the analysis period of interest.

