**6.7.2. *Historical Illness and Preexisting Conditions***

Historical illnesses and preexisting conditions will be classified using the latest version of MedDRA.

Historical illness/condition is defined as the condition/event recorded on the *Preeexisting Conditions and Medical History* eCRF page or on the *Prespecified Medical History* eCRF page with an end date prior to the date of informed consent.

Preeexisting condition is defined as the condition/event recorded on the *Preeexisting Conditions and Medical History* eCRF page or on the *Prespecified Medical History* eCRF page with a start date prior to the date of informed consent, and no end date (ie, the event is ongoing) or an end date on or after the date of informed consent. Note, if a preexisting condition worsens in severity on or after the date of informed consent, it will be recorded as an AE on the *Adverse Events* eCRF page from the date of worsening onwards.

The summaries as described in Section 6.1 for the following conditions will be provided for the All Entered Patients, and RW ITT Population:

- Historical illnesses by treatment group and overall, by System Organ Class (SOC) and preferred term (PT).
- Preeexisting conditions by treatment group and overall, by SOC and PT.
- Prespecified medical history (hypertension; diabetes mellitus, Type I; diabetes mellitus, Type II insulin dependent; diabetes mellitus, Type II non-insulin dependent; coronary artery disease; history of stroke; dyslipidemia; psoriatic arthritis) by treatment group and overall.

The comparisons among treatment groups for RW ITT Population will be conducted using Fisher's exact test.

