## 6.13. Safety Analyses

Safety will be assessed by summarizing and analyzing AEs, laboratory analytes, vital signs, QIDS-SR16, and the Columbia Suicide Severity Rating Scale (C-SSRS). The duration of treatment exposure will also be summarized.

For Period 2, safety data will be summarized for the RW Safety Population. Treatment group comparisons will be performed on categorical safety data using Fisher's exact test, and continuous safety data will be analyzed by an ANCOVA model as described in Section [6.1.3](#).

For Combined Periods 1 and 2 (Lead-In Period Safety Population), Combined Periods 1, 2, and 3 (Lead-In Period Safety Population), Period 2 (RW Safety Population), and Period 4 (Follow-Up Period Population), the above safety variables will be summarized as described in Sections [6.1.3](#), [6.1.4](#), and [6.1.6](#), respectively.

For safety analyses, unless otherwise specified, the following baselines will be used:

- Treatment-emergent adverse events for RW Safety Population during Period 2:
  - The baseline is events ongoing prior to the first injection in Period 2.
- Treatment-emergent adverse events for Lead-In Period Safety Population during Combined Periods 1 and 2, and Combined Periods 1, 2, and 3:
  - For patients who were not randomized to placebo at Week 24, the baseline is the events ongoing prior to the first injection in Period 1;
  - For patients who are randomized to placebo at Week 24 and then are retreated with ixekizumab, the baseline for TEAEs during Period 1 is the events ongoing just prior to the first injection in Period 1, but the baseline for TEAEs after retreatment of ixekizumab is the events ongoing just prior to the first injection of retreatment during Periods 2 and 3 Combined.
- Change from baseline to minimum/maximum postbaseline, to last observation and to each scheduled postbaseline visit for laboratory and vital signs, and for treatment-emergent abnormal laboratory and vitals, including shift tables (hepatic or cytopenia labs) and the elevation of hepatic labs:
  - For Lead-In Period Safety Population during Combined Periods 1 and 2, and Combined Periods 1, 2, and 3, the baseline is the last nonmissing value prior to the first injection in Period 1 regardless of changes of treatment regimen;

- For RW Safety Population during Period 2, the baseline is the last nonmissing value prior to the first injection in Period 2.

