### 6.13.2. Adverse Events

Adverse events (AEs) will be classified based upon the latest version of the MedDRA. Adverse events will be recorded at every study visit. Any condition starting on or after the date of informed consent will be considered an AE. Any preexisting condition which worsens in severity on or after the date of informed consent will be considered and recorded as an AE on the *Adverse Event (AE)* eCRF page from the date of worsening onwards.

A treatment-emergent adverse event (TEAE) is defined as an event that first occurred or worsened in severity after baseline and on or prior to the date of the last visit within the defined treatment period. Both the date/time of the event and the date/time of the dose (that is, injection) are considered when determining TEAEs. Treatment-emergent AEs will be assigned to the study period to which it's considered treatment-emergent:

- The MedDRA lowest level term (LLT) will be used when classifying AEs as treatment-emergent.
- The maximum severity recorded for each LLT prior to the first dose date/time in the treatment Period will be used as the pre-treatment severity for that LLT. If an event during the baseline period has missing severity, and the event persists during the treatment period, then it will be considered as treatment-emergent, regardless of the postbaseline level of severity. Events with a missing severity during the treatment period will be considered as treatment-emergent.
- AEs with a particular LLT will be classified as treatment-emergent if they first start on or after the first dose date/time in the treatment period (ie, a patient has no preexisting conditions with that lowest level term), or if the severity is greater than the pre-treatment severity for that lowest level term. If a partial AE start date/time is present, the date/time will be compared as far as possible to the treatment start date/time in order to determine whether the event is treatment-emergent or not. If there is any doubt, the event will be flagged as treatment-emergent.

A follow-up emergent adverse event (FEAE) is defined as an event that first occurred or worsened in severity after the date of Visit 14 (Group A) or Visit 519 (Group B) (that is, Week 104) or the ETV:

- The MedDRA LLT will be used when classifying AEs as follow-up emergent.

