- For AEs that are ongoing at the date of Visit in Week 104 or ETV, the maximum severity recorded for each LLT on or prior to the date of the Visit at Week 104 or ETV will be used as the follow-up baseline severity for that LLT.

If a partial or completely missing AE start date/time or end date/time is present, the following imputation rules will be utilized in the analysis:

- For the start date:
  - If year, month, and day are missing, then use the earlier of the patient's first visit date or the consent date.
  - If either month or month and day are missing, then use January 1.
  - If only day is missing, impute the first day of the month.
- For the start time:
  - Impose as 23:59
- For the end date:
  - If year, month, and day are missing, then use the patient's last visit date in the follow-up period.
  - If either month or month and day are missing, then use December 31.
  - If only day is missing, then use the last day of the month.
  - The imputed date will not be beyond the patient's last visit date in the follow-up period.
- For the end time:
  - Impose as 23:59.

- If there is any doubt, the event will be flagged as treatment-emergent or follow-up emergent according to the corresponding study period. If a follow-up emergent event is already counted as treatment-emergent during the prior treatment period, it will not be counted as a follow-up emergent event.

Adverse events and TEAEs will be summarized for the following study periods by treatment groups (see [Table RHBY.6.1](#)) and analysis populations, treatment comparisons between treatment groups in Period 2 will be conducted using a Fisher's exact test:

- Combined Periods 1 and 2, Combined Periods 1, 2, and 3 (Lead-In Period Safety Population)
- Period 2 (RW Safety Population).

The following summaries/analyses will be performed:

- An overall summary of AEs including the number and percentage of patients who experienced TEAE, TEAE by maximum severity, death, SAE, TEAE possibly related to study treatment occurring in  $\geq 5\%$  of patients in the total ixekizumab group, SAE judged by investigator as possibly study treatment related (for combined periods only), discontinuations from the treatment due to an AE, and TEAEs of special interest.
- TEAE by SOC and PT.
- TEAE by maximum severity, SOC, and PT.

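### SAP 6.13 and 6.13.2 set different baselines for Period 2 TEAEs, so whether a resolved Period 1 event masks a same-term recurrence of equal or lower severity is left open

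*SAP*

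**What the plan says.** SAP 6.13 lists the safety baselines. For TEAEs in the RW Safety Population during Period 2 it states: "The baseline is events ongoing prior to the first injection in Period 2".

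SAP 6.13.2 defines a TEAE as "an event that first occurred or worsened in severity after baseline" and then gives the working rule by LLT. The comparison severity is set thus: "The maximum severity recorded for each LLT prior to the first dose date/time in the treatment Period will be used as the pre-treatment severity". An event qualifies if it first starts in the period, explained as "ie, a patient has no preexisting conditions with that lowest level term", or if it is more severe than the pre-treatment severity.

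The follow-up-emergent rule in the same section uses a similar maximum but restricts it: "For AEs that are ongoing at the date of Visit in Week 104 or ETV, the maximum severity recorded for each LLT".

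SAP 6.1 adds a general definition for safety analyses that use a baseline period: "the baseline period is defined as the entire period, that there is no drug dispensed in".

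Protocol 10.3.4 bases the primary safety analyses on the RW Safety Population in Period 2. SAP 6.13.2 compares the arms there by Fisher's exact test.

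**The concern.** All patients receive ixekizumab during the 24-week lead-in (Protocol 5.1), and adverse events are recorded throughout. The look-back in 6.13.2 therefore reaches into time on drug. It can treat a reaction that occurred on ixekizumab, and resolved, as pre-treatment history for Period 2.

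If that reading is programmed, a patient with a mild injection-site reaction in Period 1 and another mild one with the same LLT in Period 2 does not appear in the Period 2 TEAE table. If the 6.13 baseline is programmed, the same patient does appear. Events that recur on continued drug are part of what a comparison of continued treatment with withdrawal should show. Two programmers following the same SAP could deliver different tables.

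**Working it through.** The plan states no figure on this point, so there is nothing to reproduce. The check sets the rules side by side, works a test case, and then illustrates size on assumed inputs.

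**1. Which baseline the SAP uses elsewhere**

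| Place | Look-back for adverse events |
|---|---|
| SAP 6.13, Period 2 | ongoing events only |
| SAP 6.1.2.1, after retreatment | ongoing events only |
| SAP 6.1.5.2, Period 3 | ongoing events only |
| SAP 6.13.2, follow-up rule | ongoing events only, at their maximum severity to date |
| SAP 6.13.2, TEAE rule | any earlier record of the LLT |

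Only the TEAE classification rule lacks the restriction.

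**2. Test case.** A moderate event in Period 1 resolves. An event with the same LLT starts in Period 2.

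| Period 2 severity | TEAE under 6.13.2 look-back | TEAE under 6.13 baseline |
|---|---|---|
| mild | no | yes |
| moderate | no | yes |
| severe | yes | yes |

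The rules disagree whenever the recurrence is no more severe than the earlier event.

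**3. Size, on assumed inputs.** Let p be the share of patients with the term in Period 1 (all resolved by Week 24). Let R be the Period 2 risk in those patients relative to the rest, and q the probability that the recurrence is no more severe. Then

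missed share of patients with a Period 2 event = q × pR / (pR + 1 − p).

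The upper q is 1. The lower q assumes independent severities split 50% mild, 42% moderate and 8% severe: 0.50×0.50 + 0.42×0.92 + 0.08×1.00 = 0.716.

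| p | R | pR/(pR + 1 − p) | missed (q = 0.716 to 1) |
|---|---|---|---|
| 0.02 | 1 | 0.02/1.00 = 0.020 | 1.4% to 2.0% |
| 0.05 | 1 | 0.05/1.00 = 0.050 | 3.6% to 5.0% |
| 0.10 | 2 | 0.20/1.10 = 0.182 | 13% to 18% |
| 0.15 | 4 | 0.60/1.45 = 0.414 | 30% to 41% |

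**4. Effect on the contrast, also assumed.** Let 10% of each arm have the term in Period 1, with no recurrence more severe. Placebo risk in Period 2 is 5% whatever the history.

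- Ixekizumab recurrence 30%, new onset 10%: true rates are 0.10×0.30 + 0.90×0.10 = 12% against 5%. With the look-back they are 9% against 0.90×0.05 = 4.5%. The difference falls from 7 to 4.5 points and the ratio from 2.4 to 2.0.
- Ixekizumab 10% for both: true rates are 10% against 5%. With the look-back they are 9% against 4.5%. The ratio stays at 2.0 and the difference falls from 5 to 4.5 points.

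Marked attenuation therefore depends on recurrence being more drug-related than new onset, which the documents do not tell us.

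**The case against.** The strongest reply is that the SAP, read as a whole, already counts the recurrence. The TEAE definition is relative to baseline, and 6.13 says what that baseline is. SAP 6.7.2 describes a preexisting condition as one "with a start date prior to the date of informed consent, and no end date" or with an end date on or after consent, so an event that began and resolved in Period 1 is not one. Protocol Appendix 1 defines a TEAE as something that occurs or worsens after treatment baseline. This stands as far as it goes: a programmer could defensibly count the recurrence, and a reader who infers that the plan definitely removes such events goes too far. But none of these places cancels the explicit look-back in 6.13.2. The section's instruction to flag doubtful events follows its sentence on partial dates and does not clearly settle the matter.

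Other limits also stand:

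- The drug-free baseline period in SAP 6.1 is a general statement that yields to the specific baselines in 6.13. It fits Period 2 poorly but is not the core conflict.
- Masking needs the same LLT at equal or lower severity. A different infection term in Period 2 still counts.
- SAEs, events leading to discontinuation and the by-patient listing of all events (SAP 6.13.2 and 6.13.3) are not described as restricted to TEAEs.
- A reader might put the loss at 24% to 37% by taking recurrence r of 30% to 50%, p of 5% to 15%, and new onset in Period 2 equal to p: pr / (pr + (1 − p)p). Period 2 lasts 40 weeks against 24. Scaling new onset at constant hazard to 1 − (1 − p)^(40/24), that is 0.082 and 0.237, gives 0.015/(0.015 + 0.95×0.082) = 16% up to 0.075/(0.075 + 0.85×0.237) = 27%. Early retreatment, which ends Period 2 for this population, would reduce that correction. None of these inputs comes from the documents.

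**Conclusion.** The two sections conflict, and the SAP as written supports two codings of the same Period 2 event. The point concerns the Period 2 TEAE tables and the TEAE-based summaries of events of special interest, such as hypersensitivity and injection-site reactions in Table RHBY.6.8.

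The arms share the same kind of Period 1 history, so the look-back lowers counts in all of them and does not by itself favour one. It could attenuate a real difference if recurrence is drug-related. A reader might infer that the ixekizumab-placebo contrast is known to be pulled toward zero, but the documents do not show this. The size is unknown: the 1% to 41% range rests wholly on the assumed p, R and q above. The point deserves correction because the primary safety table should not depend on a programmer's choice, not because a bias of known size has been shown.

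**What to change.** In SAP 6.13.2, for Period 2:

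- Define the pre-treatment severity as the maximum severity, up to the first Period 2 dose, of events with that LLT that are ongoing at that dose.
- Count an event as treatment-emergent if it starts on or after that dose and either no event with that LLT was ongoing at the dose or the ongoing one ended before the new onset. Also count it if its severity exceeds the pre-treatment severity.
- State that a continuing event re-entered at equal or lower severity is not treatment-emergent. Protocol 9.2 has sites record changes in a condition as adverse events, so simply counting every start date after the dose would bring in events that are neither new nor worse.
- State that for Period 2 adverse events the baseline period means the events ongoing at the first Period 2 dose, not the drug-free period of SAP 6.1. The rule for missing baseline severity in 6.13.2 then keeps something to refer to.

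Start and stop dates are already collected (Protocol 9.2). The cost is revised SAP wording, minor reprogramming and somewhat higher TEAE percentages in all arms.

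### SAP 6.13.2 counts worsening after Week 104 or the ETV as follow-up emergent, then excludes any such event already counted as treatment-emergent, so the only Period 4 adverse event table omits that worsening

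*SAP*

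**What the plan says.** All the relevant rules are in SAP 6.13.2.

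- **TEAE.** The trigger and its time window are given as: "first occurred or worsened in severity after baseline and on or prior to the date of the last visit within the defined treatment period".
- **FEAE.** "A follow-up emergent adverse event (FEAE) is defined as an event that first occurred or worsened in severity after the date of Visit 14" for Group A, or the corresponding Group B visit, or the ETV. Events are classified by MedDRA lowest level term (LLT).
- **Follow-up baseline severity.** For events ongoing at that visit, "the maximum severity recorded for each LLT on or prior to the date of the Visit at Week 104 or ETV" serves as the reference level.
- **Exclusion.** The last bullet of the rules for partial or missing dates begins: "If there is any doubt, the event will be flagged as treatment-emergent or follow-up emergent according to the corresponding study period". It continues: "If a follow-up emergent event is already counted as treatment-emergent during the prior treatment period, it will not be counted as a follow-up emergent event".

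For output, TEAEs are tabulated by system organ class and preferred term (PT), and also by maximum severity. FEAEs are tabulated for the Follow-Up Period Population by PT only. A by-patient listing of all adverse events is also planned.

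**The concern.** A follow-up baseline severity for ongoing events has one use: deciding whether an event got worse in follow-up. An event that starts on treatment, is counted as a TEAE and is still ongoing at Week 104 or the ETV is a typical case for that rule. The exclusion sentence takes exactly that case out, because the event is already counted as treatment-emergent. One part of the section builds a comparison that a later sentence cancels for most of the events that arise on treatment.

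Protocol 5.4 describes Period 4 as important for safety monitoring while ixekizumab clears. The FEAE-by-PT table is where adverse events in that period are counted by treatment group. If it omits worsening of events that began on treatment, a reader of the tables would not see, for example, an infection that was mild at the last treatment-period visit and became worse afterwards. In addition, two programmers working from the same SAP could produce different Period 4 counts.

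**Working it through.** No sample size, power or event count is involved, so the check applies the definitions and the exclusion sentence, as written, to each possible course of an adverse event.

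| Course of the event | In the TEAE table? | FEAE by definition? | FEAE after the exclusion? |
|---|---|---|---|
| 1. Preexisting, no worse on treatment, worse in Period 4 | No | Yes | Yes |
| 2. New on treatment, worse in Period 4 | Yes | Yes | **No** |
| 3. Preexisting, worse on treatment, worse again in Period 4 | Yes | Yes | **No** |
| 4. New in Period 4 | No | Yes | Yes |
| 5. New or worse on treatment, no worse in Period 4 | Yes | No | No |

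The definition and the exclusion disagree in courses 2 and 3 only. In both, the event itself stays in the TEAE table. The later worsening is dated after the TEAE window has closed, and the exclusion blocks it from the FEAE count.

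Next, whether another planned summary picks up the worsening in courses 2 and 3:

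- SAP 6.13.3: the tables of serious adverse events (SAEs) and of events leading to discontinuation cover Combined Periods 1 and 2, Combined Periods 1, 2 and 3, and Period 2. Period 4 is not among them.
- SAP 6.13.3.1: in general no summary of events of special interest is given for Period 4, apart from hepatic laboratory tests.
- SAP 6.13.2 and 6.13.3: by-patient listings of all adverse events, deaths and SAEs would show it, but without counts by treatment group.
- SAP 6.19: the registry output counts SAEs whether or not they are TEAEs, so a serious worsening would be included there.
- SAP 6.13.4 and 6.13.4.2: follow-up emergent laboratory abnormalities and neutrophil recovery are summarized for Period 4. A cytopenia is therefore covered by another route; an infection is not.

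So a non-serious worsening of a TEAE, with no laboratory counterpart, would be found only in the listings.

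**The case against.** The strongest reply is that the exclusion sentence was never meant to govern worsening. It closes the bullets on partial and missing dates and directly follows the sentence on doubtful cases. In that place it works as a tie-breaker against counting one occurrence twice, and the definition and the follow-up baseline severity stay in force. This reading is plausible, but the sentence carries no date condition and the SAP does not say which reading applies. The ambiguity still has to be settled.

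A second reply concerns how the data are recorded. SAP 6.13.2 says that worsening of a preexisting condition is recorded as an adverse event from the date of worsening. If worsening of a TEAE were also entered as a new record, that record might not count as already treatment-emergent. If instead one record carries its worst grade, the table of TEAEs by maximum severity might show the later grade, since the SAP does not say that severity is cut off at the last visit. Both points stand as possibilities. The SAP makes no such recording statement for TEAEs, and classification is by LLT, which makes the literal exclusion easy to apply.

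A reader might go further and infer that these events vanish from both tables. They do not: the exclusion acts only on events already counted as TEAEs, so none is missing from both. A reader might also infer that the worsening part of the FEAE definition is left with almost nothing to count. That is too strong. Under the Schedule of Activities in the protocol (Section 2, footnote j), adverse events still ongoing from the originating study are preexisting conditions in this study, and those that first worsen in Period 4 remain FEAEs.

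**Conclusion.** As written, SAP 6.13.2 is internally inconsistent and should be corrected. On the literal reading, worsening in Period 4 of an event already counted as a TEAE is left out of the FEAE-by-PT table.

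The effect is confined to that one table, which is descriptive: Table RHBY.6.1 specifies no inferential statistics for Period 4. No hypothesis test, error rate or power is touched. The number of patients affected cannot be estimated, because the documents give neither the proportion with a TEAE ongoing at Week 104 or the ETV nor the proportion of those who worsen. The approximately 750 patients expected to enter the study are not a suitable denominator either, since some patients need not enter Period 4 (Protocol 5.1).

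It would be tempting to conclude that the plan hides harm after treatment ends. The documents do not support that: the listings, the registry SAE counts and the Period 4 laboratory summaries remain. The conclusion rests on taking the exclusion at its word. If it was meant only for uncertain dates, the intended analysis is sound and only the text needs repair.

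**What to change.** Restrict the exclusion with one condition, for example: *An event already counted as treatment-emergent is counted as follow-up emergent only if its severity in Period 4 exceeds its follow-up baseline severity for that LLT.* This uses a quantity that the SAP already derives and restores the section's own definition. The exclusion still applies to ongoing events that have not changed and to events whose dates are uncertain.

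The cost is one SAP sentence and one programming condition. A few patients will appear in both the TEAE and FEAE tables for the same term, which a footnote can explain. Because the FEAE table is by PT only, the grade reached would still be seen only in the listings; adding maximum severity to that table would show it.
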